#### **5.6. PER PROTOCOL POPULATION**

The per-protocol population (PP) will contain all subjects from the EFF, where subjects with major deviations potentially having an impact on the efficacy endpoints will be assessed, flagged and excluded from this analysis population. The final list of protocol deviations resulting in exclusion of a subject from the PP will be determined and approved prior to DBL of the Main Study.

This population will be used to perform sensitivity analyses for the primary and secondary efficacy endpoints.

### **6. GENERAL CONSIDERATIONS**

Categorical variables will be reported as frequency and percent. Continuous variables will be reported as number of subjects with available data (n), mean, SD, median, minimum, and maximum.

## 6.1. STUDY DAY AND PERIOD DAY

Two different types of study days will be calculated for this study:

- 1) Study Day will be calculated based on the date of the first dose of OL study drug in the OL OTTP and will be used to show start and stop days of assessments and events during the study. Study Day 1 will be the day of the first dose of OL study drug in the OTTP.
- 2) Period Day will be calculated based on the date of the start of the study period during which the assessments or events will be performed or occur to show start and stop days of assessments or events during the study period.

Study Days will be calculated as follows:

- Study Day= (date of assessment or event – date of first dose of OL study drug in the OTTP) if the date of assessment or event is before the date of first dose of OL study drug during the OTTP
- Study Day= (date of assessment or event – date of first dose of OL study drug in the OTTP) + 1 if the date of assessment or event is on or after the date of first dose of OL study drug during the OTTP

Period Days of each study period will be calculated as follows:

Efficacy Data:

- OL OTTP Day= (date of assessment or event – start date of Visit 2) + 1
- OL SDP Day= (date of assessment or event – start date of Visit 14) + 1
- DB RWP Day= (date of assessment or event – date of randomization) + 1
- OLE Day= (date of assessment or event – start date of Visit 19 for re-entry or end date of Visit 16 for rollover subjects) + 1

Safety Data:

- OL OTTP Day= (date of assessment or event – start date of first dose of OL study drug in the OTTP) + 1
- OL SDP Day= (date of assessment or event – date of the first dose of OL study drug in the SDP) + 1
- DB RWP Day= (date of assessment or event – date of the first dose of DB study drug in the DB RWP) + 1
- OLE Day= (date of assessment or event – date of the first dose of OL study drug in the OLE) + 1

## 6.2. BASELINE

- **Weekly average of Cataplexy Attacks:** For this efficacy endpoint, baseline will be defined as the average number of daily cataplexy attacks from days with non-missing data within the 2 weeks OL SDP, multiplied by 7.

- **Epworth Sleepiness Scale (ESS), 36-Item Short Form Health Survey (SF-36), and European Quality of Life (EuroQoL) 5 Dimensions 5 Levels (EQ-5D-5L):** For these assessments, baseline will be defined as the last non-missing measurement taken prior to or on the date of randomization (including unscheduled assessment) i.e., DB RWP Day 1.
- **Clinician Global Impression of Severity (CGIs) for Narcolepsy Overall:** For this assessment, no baseline will be defined as this scale will be collected only once during the study i.e., at the end of the OL SDP.
- **Patient Global Impression of Change (PGIc) for Narcolepsy Overall and Clinician Global Impression of Change (CGIc) for Narcolepsy Overall:** For these assessments, no baseline will be defined as these scales already assess the change in the severity of the subject’s narcolepsy overall since the end of the OL SDP. Furthermore, these assessments will be recorded only once during the study, i.e., at the end of the DB RWP.
- **Hematology, Fasting Chemistry (incl. electrolytes), Weight, Vital signs, Urine Drug Screen, Columbia-Suicide Severity Rating Scale (C-SSRS), Physical Examination, 12-Lead Electrocardiogram (ECG) and Patient Health Questionnaire-9 (PHQ-9):** For these assessments, two types of baseline will be defined:
  1. ‘Main Study baseline’ will be defined as the last non-missing measurement collected/ assessed prior to or on the same day of the first dose of study drug during the Main Study, including unscheduled measurements and retests.
  2. ‘OLE baseline’ will be defined as the last non-missing measurement collected/ assessed prior to or on the same day of the first dose of study drug during the OLE, including unscheduled measurements and retests.

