	6. If currently being treated with Xyrem, the subject's total twice nightly Xyrem dose must be no higher than 9 g/night
OPEN-LABEL EXTENSION	·
DIAGNOSIS AND MAIN	
CRITERIA FOR EXCLUSION	Subjects will be excluded from re-entering the study at the Open-Label Extension if they:
	1. Meet Exclusion Criteria 1 through 19 from the Main Study at Visits 18 and 19.
	2. Received any investigational drug (with the exception of JZP-258) within 30 days or 5 half-lives (whichever is longer) before the Screening Visit.
	Allergy or sensitivity to malic acid, sucralose or ingredients in the study drug formulation.
TEST PRODUCT	JZP-258 oral solution 0.5 g/mL
REFERENCE PRODUCT	JZP-258 Placebo, identical in appearance to JZP-258
DURATION OF TREATMENT	The maximum treatment duration for each subject who does not enter the Open-Label Extension will be up to 16 weeks including 12 weeks Optimized Treatment and Titration Period, 2 weeks Stable-Dose Period, 2 weeks Double-Blind Randomized-Withdrawal Period, and this is followed by a 2 week Safety Follow-up period. The treatment period for subjects who do enter the Open-Label Extension will be up to
	40 weeks, which is followed by a 2-week Safety Follow-up Period.

Confidential Page 8 of 148

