The inclusion of a placebo control group in this study is necessary to determine the efficacy and safety of this new investigational medicinal product. Although effective doses of JZP-258 may be observed during Open-Label-Titration and Stable-Dose Periods of the study, the definitive efficacy effect can be determined only after double-blind comparison with placebo, considering the slightly different pharmacokinetic profile of JZP-258 (lower C_{max} versus Xyrem). The risks of placebo exposure were taken into consideration during the protocol design. The incorporation of a short 2-week, randomized-withdrawal phase into the study may allow the demonstration of the efficacy of JZP-258 as measured by the recurrence of cataplexy symptoms without extensive placebo burden to the subjects. In this 16 week long study, the maximal time during the Main Study that any subject will be exposed to placebo is 2 weeks (12.5% of total exposure time). Furthermore, the recurrence of cataplexy during these two weeks, as pointed out above, is considered minimal to obtain statistically significant efficacy data compared to placebo. Importantly, in the case of emergency situations, as per Section 6.13.9 of the protocol, the Investigator will be able to unblind a subject at any time for immediate medical management of the subject, if necessary.

Confidential Page 39 of 148

Jazz has recently modified the protocol (Amendment 4) to include a six month Open-Label Extension to the study to allow subjects who have completed the Double-Blind Randomized Treatment portion of the study to continue or re-enroll into the study and receive open-label JZP-258. This extension period was added to provide additional treatment benefit for subjects as well as to assess longer term safety with JZP-258.

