## 9.9. SAFETY OUTCOMES

In general, safety outcomes will be summarized across all study periods by visit overall, and by Pre-Randomization Group based on SAF. Data collected while subjects randomized to placebo were on placebo will be excluded from this summaries.

Data will also be summarized overall and by treatment group based on the DB RWP SAF.

No inferential statistics will be performed; only summary statistics will be provided unless otherwise noted.

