## 9.9.2. LABORATORY EVALUATIONS

Results from the central laboratory will be included in the reporting of this study for:

- **Hematology, Serum chemistry (excluding electrolytes):** Main Study baseline, end of DB RWP, OLE baseline, and end of OLE Period
- **Electrolytes (i.e., sodium, potassium, magnesium, and calcium):** Main Study baseline, each Main Study in-clinic scheduled visit, OLE baseline, OLE Week 12, and end of OLE Period
- **Urinalysis:** Main Study baseline, end of DB RWP, OLE baseline, and end of OLE Period
- **Pregnancy test:** serum at Main Study screening visit, urine at each Main Study in-clinic scheduled visit, serum at OLE screening visit, and urine at each OLE in-clinic scheduled visit
- **Drug screen:** Main Study screening visit, each Main Study in-clinic scheduled visit, OLE screening visit, and each OLE in-clinic scheduled visit
- **Alcohol screen:** Main Study screening visit, each Main Study in-clinic scheduled visit, OLE screening visit, and each OLE in-clinic scheduled visit

An authorized back-up laboratory may be used if necessary as an emergency laboratory. A list of laboratory assessments to be included in the outputs is included in APPENDIX 5.

See section 6.3 for handling of retests and unscheduled measurements.

Laboratory results will be reported in SI Units.

For **hematology, serum chemistry, electrolytes** and **urinalysis data** the following summaries will be provided across all study periods by visit:

- Observed and change from baseline (Main Study baseline and OLE baseline) for quantitative measurements
- Observed for qualitative measurements

- Shift table from baseline (Main Study baseline and OLE baseline) according to normal reference range criteria (for quantitative measurements)

The same summaries will be repeated on the RWP SAF by treatment group.

For hematology, serum chemistry, electrolytes and urinalysis data, the summaries of change from baseline during the OLE will differ depending on subjects:

- For rollover subjects: change from baseline = OLE measurements – Main Baseline
- For re-entry subjects: change from baseline = OLE measurements – OLE Baseline

For electrolytes, a box plot of change from baseline will also be provided by pre-randomization group across all study periods based on the SAF.

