### 9.9.5.2. PATIENT HEALTH QUESTIONNAIRE-9

The PHQ-9 is a nine-item depression scale developed based on the nine diagnostic criteria for major depressive disorder in the Diagnostic and Statistical Manual Fourth Edition (DSM-IV) (Kroenke *et al* 2001, Kroenke *et al* 2010). Responses to each item range from 0 = not at all to 3 = nearly every day. The instrument can be administered in person, by telephone or can be self-administered and is used to facilitate diagnosis of major depression and assessment of symptom severity. The PHQ-9 will be assessed at Main Study screening visit, start of the OL OTTP visit (day 1), week 2, week 4, week 6, week 8, week 10, end of OL OTTP visit (week 12), end of OL SDP visit (week 14), end of DB RWP/ Early Termination visit (week 16), Main Study Safety Follow-up visit (week 18), OLE screening visit, OLE week 12, end of OLE/Early Termination visit (OLE week 24), and OLE Safety Follow-up visit (week 26).

The PHQ-9 total score is the sum of 9 item-scores and can range between 0 and 27 with higher scores indicating greater severity of depression (1-4 = minimal depression; 5-9 = mild depression; 10-14 = moderate depression; 15-19 = moderately severe depression; and 20-27 = severe depression). If 3 or

more items are left unanswered, the total score will not be computed. If 1 or 2 items are left unanswered, a prorated score will be calculated. The prorated score is calculated as the sum of the scores of the items that were answered to get a partial raw score. Then, the partial raw score will be multiplied by the total number of items on the PHQ-9 (i.e., 9) and divided by the number of items that were actually answered (i.e., 7 or 8). If the result is a fraction, it will be rounded to the nearest whole number.

PHQ-9 total score and change from baseline (Main Study baseline and OLE baseline) will be tabulated by visit across all study periods by pre-randomization group and by treatment group.

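### By-arm safety changes in the 2-week double-blind period are measured from before open-label dosing, although Visit 15 values exist for electrolytes, weight, vital signs and PHQ-9

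*SAP*

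**What the plan says.** SAP 6.2 treats hematology, chemistry with electrolytes, weight, vital signs, ECG, C-SSRS, PHQ-9 and some other safety items together: "For these assessments, two types of baseline will be defined". The Main Study baseline is "the last non-missing measurement collected/ assessed prior to or on the same day of the first dose of study drug during the Main Study". The other is its counterpart for the open-label extension (OLE). In the same section, ESS, SF-36 and EQ-5D-5L are anchored to the last value on or before randomization.

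By-arm safety summaries are planned for the double-blind randomized-withdrawal period (RWP):

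- SAP 9.9, for safety data in general: "Data will also be summarized overall and by treatment group based on the DB RWP SAF".
- SAP 9.9.2, for laboratory data: "Observed and change from baseline (Main Study baseline and OLE baseline) for quantitative measurements", with shift tables from the same two baselines. It then adds: "The same summaries will be repeated on the RWP SAF by treatment group".
- SAP 9.9.5.2: "PHQ-9 total score and change from baseline (Main Study baseline and OLE baseline) will be tabulated by visit", by treatment group among other splits.
- SAP 9.9.4.1 and Table 4 define markedly abnormal vital signs and weight against the same two baselines. SAP 9.9.4 names these summaries only across study periods, so a by-arm version follows only from the general sentence in 9.9.

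Protocol 7.1.4 and Appendix 1.1 collect weight, vital signs, electrolytes, PHQ-9 and C-SSRS at Visit 15. The note under SAP Table 2 says that the drug for a period is taken only after that day's scheduled assessments.

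**The concern.** The randomized question for these measures is what happens over two weeks when JZP-258 is continued or replaced by placebo. The planned change answers a different question: what has happened since before open-label dosing. A shift that arose during titration and then stayed constant will appear in the double-blind tables of both arms. A shift that reversed on withdrawal will appear as no change on placebo.

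The Day 1 reference also differs between strata. Pre-randomization Groups 1 and 2 enter on Xyrem and switch gram for gram on Day 1, while Groups 3 and 4 enter without Xyrem. For electrolytes this matters, since Protocol 1.1 puts the sodium load of 9 g Xyrem at 1.64 g per day. The change from Day 1 thus mixes a formulation switch, a drug start and the randomized withdrawal.

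The SAP already uses the right anchor elsewhere. The efficacy scales use the value at randomization, and double-blind TEAEs (SAP 9.9.1) count from the first double-blind dose.

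**Working it through.** **1. The plan's own figure.** The Protocol synopsis describes treatment as "including 12 weeks Optimized Treatment and Titration Period, 2 weeks Stable-Dose Period, 2 weeks Double-Blind Randomized-Withdrawal Period". That is 12 + 2 + 2 = 16 weeks, and 2/16 = 12.5%, which agrees with the share in Protocol 3.1.3. The remainder is 14/16 = 87.5%, all of it open-label JZP-258 in both arms.

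**2. Which baseline applies at Visit 16.** The OLE baseline is taken at or after the end of double-blind treatment, so only the Main Study baseline can serve.

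- Measures taken on Day 1: 16 × 7 = 112 days to Visit 16, of which 14 are double-blind (14/112 = 12.5%).
- Measures taken only at screening (Day −30 to −1): 112 + 1 = 113 to 112 + 30 = 142 days, so the double-blind share is 14/113 = 12.4% down to 14/142 = 9.9%. With the permitted 2-week screening extension it is 14/156 = 9.0%.

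**3. Where a Visit 15 value exists.**

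| Measure | Scheduled at Visit 15 | Planned by-arm summary affected |
|---|---|---|
| Electrolytes | Yes | Change and shift |
| PHQ-9 total | Yes | Change |
| Weight, vital signs | Yes | Change, and markedly abnormal counts if produced by arm |
| C-SSRS | Yes | None: counts, no change from baseline |
| Hematology, other chemistry, urinalysis, ECG | No (Protocol 6.6, 6.10.2) | Early baseline unavoidable |

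**4. Difference between arms.** Let *a* be the mean open-label shift and *f* the fraction of it reversed on placebo within two weeks.

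- From Day 1: JZP-258 shows *a*, placebo shows *a*(1 − *f*), difference *af*.
- From Visit 15: JZP-258 shows 0, placebo shows −*af*, difference *af*.

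The difference is the same. The within-arm figures are not. With *f* = 0.5 and *a* = 1, Day 1 gives 1 and 0.5, while Visit 15 gives 0 and −0.5.

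**5. Threshold counts.** In Table 4 the weight criterion is purely a change of at least 7.0% in either direction. A subject who lost 7% during open-label treatment and then stayed flat would be counted at Visit 16 in a by-arm table, on placebo as well as on JZP-258. Measured from Visit 15, the change is 0% and the subject is not counted. Shift tables behave in the same way.

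**6. Precision.** With equal variance σ² at each visit, the SD of change is σ√(2(1 − ρ)). The ratio of Day 1 to Visit 15 is √((1 − ρ₁)/(1 − ρ₁₅)), where ρ₁ and ρ₁₅ are the correlations of the Day 1 and Visit 15 values with Visit 16. The documents give neither, so these are assumptions:

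- ρ₁ = 0.6, ρ₁₅ = 0.7: √(0.4/0.3) = 1.15
- ρ₁ = 0.5, ρ₁₅ = 0.7: √(0.5/0.3) = 1.29
- ρ₁ = 0.6, ρ₁₅ = 0.8: √(0.4/0.2) = 1.41
- ρ₁ = 0.4, ρ₁₅ = 0.8: √(0.6/0.2) = 1.73
- ρ₁ = 0.8, ρ₁₅ = 0.9: √(0.2/0.1) = 1.41
- ρ₁ = 0.7, ρ₁₅ = 0.9: √(0.3/0.1) = 1.73

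**The case against.** A reader might infer that the randomized safety comparison is biased, or cannot show what happened in the double-blind period. The documents do not support that. Both arms pass through the same open-label run-in and are randomized after it, so the earlier shift cancels in expectation (step 4). Nor is this the only randomized safety comparison: double-blind TEAEs are summarized by arm and correctly anchored. Safety data are not tested, so no error rate or decision rule depends on the baseline.

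Part of the 2-week change may also be recoverable. SAP Table 2 gives the end of the Stable-Dose Period its own window for these measures, and summaries are by visit. If the by-arm tables show both Visit 15 and Visit 16, a reader can subtract the means for subjects with both values. This stands, but it yields neither the SD of the 2-week change nor shift and threshold counts from Visit 15. The table shells that would settle the layout are not in the documents.

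A pre-exposure baseline is also defensible in itself. Visit 15 is an on-drug value, so a Visit 15 baseline alone would miss abnormalities that JZP-258 had already caused and that persist. This stands in full, and is why the existing summaries should stay.

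C-SSRS should be left alone. It is tabulated as counts, and the Since Last Visit form at Visit 16 already covers the time since Visit 15.

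**Conclusion.** The point holds as a limited gap in the descriptive safety analysis. For electrolytes, weight, vital signs and PHQ-9, the SAP has a pre-dose value at the start of the randomized period and does not use it as a baseline. Fourteen of the 16 weeks in each Visit 16 change precede randomization. Within-arm changes and shift counts, and any by-arm markedly abnormal counts, therefore do not isolate the double-blind period. Precision is lower whenever Visit 15 correlates with Visit 16 more strongly than Day 1 does. The factor of 1.15 to 1.73 is illustrative only, because the correlations are assumed.

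It is tempting to read 87.5% as the share of the change caused by open-label JZP-258. It is a share of elapsed time, not an effect size. It says nothing about how much of a shift reverses on placebo, and in Groups 1 and 2 the Day 1 value is already on Xyrem.

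For hematology, other chemistry, urinalysis and ECG there is no scheduled Visit 15 value, so the early baseline is a limitation of the schedule that the SAP cannot remove. Efficacy analyses are not affected.

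**What to change.** In SAP 6.2, add a third safety baseline, for example 'RWP baseline': the last non-missing value on or before the first double-blind dose, for electrolytes, weight, vital signs and PHQ-9 total score. In 9.9.2, 9.9.4 and 9.9.5.2, state that by-arm change, shift and (for vital signs and weight) markedly abnormal summaries on the double-blind safety population will be shown against it, alongside the Main Study baseline versions.

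Keep the Main Study baseline alone for hematology, other chemistry, urinalysis and ECG, and note why. Leave C-SSRS unchanged.

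This is a cheap improvement. It costs one derived flag, some additional descriptive tables and a footnote explaining that two baselines are in use. No assessments or visits need to be added.

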### 6.3. WINDOWING CONVENTIONS

For the cataplexy attacks, weekly averages will be calculated using daily diary entries between the scheduled Period Days as specified in Table 1. For the OL SDP and DB RWP, averages over the 2 weeks of the study period will also be calculated. The weekly averages will not be computed for the OLE as the cataplexy frequency diary will not be collected during that part of the study.

**Table 1 Visit Windows for Assessments Recorded Daily**

Study Period	Adjusted-Defined Windows		Visit Windows
	Visit	Scheduled Period Day	
OL OTTP	Week 1	8	Study Day 1 < Period Day ≤ 8
	Week 2	15	9 ≤ Period Day ≤ 15
	Week 3	22	16 ≤ Period Day ≤ 22
	Week 4	29	23 ≤ Period Day ≤ 29
	Week 5	36	30 ≤ Period Day ≤ 36
	Week 6	43	37 ≤ Period Day ≤ 43
	Week 7	50	44 ≤ Period Day ≤ 50
	Week 8	57	51 ≤ Period Day ≤ 57
	Week 9	64	58 ≤ Period Day ≤ 64
	Week 10	71	65 ≤ Period Day ≤ 71
	Week 11	78	72 ≤ Period Day ≤ 78
	Week 12	85	79 ≤ Period Day ≤ Date of Visit 14

Statistical Analysis Plan

---

OL SDP	Week 1	8	1 < Period Day ≤ 8
	Week 2	15	9 ≤ Period Day ≤ Date of Visit 15
	Over Weeks 1 and 2	n/a	1 < Period Day ≤ Date of Visit 15
DB RWP	Week 1	8	1 < Period Day ≤ 8
	Week 2	15	9 ≤ Period Day ≤ Date of Visit 16
	Over Weeks 1 and 2	n/a	1 < Period Day ≤ Date of Visit 16

Note: DB: Double-Blind. n/a: Not Applicable. OL: Open-Label. OTTP: Optimized Treatment and Titration Period. RWP: Randomized-Withdrawal Period. SDP: Stable-Dose Period.

Note: Period Day 1 is excluded from the visit windows as the study drug will be taken only after all the assessments scheduled to be collected on that day will have been performed.

Note: For SDP longer or shorter than 14 days, use all available data from the period to calculate baseline, for DB RWP longer or shorter than 14 days, use all available data to account for efficacy.

For measurements/assessments other than cataplexy attacks, scheduled assessments will be summarized by nominal visits. Unscheduled and Early Termination visits will be mapped based on the scheduled Period Day of each visit with adjusted analysis-defined visit windows, unless otherwise specified. The adjusted analysis-defined windows are specified in [Table 2](#).

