6.12.7 Cataplexy Frequency Diary

Subjects will complete a daily Cataplexy Frequency Diary (Appendix 13) each night prior to bedtime, to record the number of cataplexy attacks that they had each day beginning at Visit 2 through the end of the Double-Blind Randomized-Withdrawal Period. Subjects must have completed the Cataplexy Frequency Diary on at least 10 out of the 14 days in the Stable-Dose Period occurring prior to the start of the Double-Blind Randomized-Withdrawal Period, or they will be discontinued from the study.

The study staff will review the diary at each study visit and discuss it with the subject at each phone contact.

> Confidential Page 59 of 148

Jazz Pharmaceuticals

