7.1.5 End of Double-Blind Randomized-Withdrawal Period or Early Termination

End of Week 16 - Visit 16

- Record weight in ordinary indoor clothes (without shoes).
- Obtain vital signs (systolic and diastolic blood pressure, heart rate and respiratory rate, and body temperature) after the subject has been resting for at least 5 minutes.
- Perform a physical examination including a full examination of body systems (excluding a full genitourinary exam) and a brief neurological examination.
- Obtain fasting blood samples for serum chemistry (including Na, K, Ca, and Mg), hematology.
- Collect urine for urinalysis and perform urine drug screen.
- Perform alcohol screen.
- Provide for a light breakfast, if needed.
- Obtain a 12-lead ECG after the subject has been resting supine for at least 5 minutes.
- Complete CGIc for narcolepsy overall.
- Have subject complete the PGIc.
- Obtain a urine pregnancy test for all females of childbearing potential (Section 6.10.1).
- Administer the following:
 - ESS
 - SF-36
 - EuroQoL
 - PHO-9
 - C-SSRS Since Last Visit version.
- Review Cataplexy Frequency Diary for completeness.
- Review the Dosing Diaries for completeness and compliance with dosing.
- Collect remaining study drug from Double-Blind Randomized-Withdrawal Period and assess compliance versus Dosing Diary.
- Record all AEs that occurred since the last visit on the AE eCRF.
- Record all concomitant medications that were taken since the last visit on the concomitant medications eCRF.
- Schedule the Safety Follow-up Visit in 2 weeks if not enrolling into the Open-Label Extension.
- Instruct subject to follow-up with their healthcare provider regarding the resumption of any medications that were discontinued prior to study participation if not enrolling into the Open-Label Extension.

Confidential Page 76 of 148

Jazz Pharmaceuticals

If a subject is withdrawn before completing the study, the reason for withdrawal will be entered on the appropriate eCRF. The specific reason for the withdrawal should be documented on the eCRF. For instance, rather than stating "withdrew informed consent", the specific reason for withdrawing the informed consent should be stated. Whenever possible and reasonable, the evaluations that were to be conducted during the final study visit should be performed at the time of premature discontinuation.

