## 9.8.1. PRIMARY EFFICACY ENDPOINT

### 9.8.1.1. PRIMARY EFFICACY ENDPOINT & DERIVATION

The primary efficacy endpoint is the change in average weekly number of cataplexy attacks from the two weeks of the OL SDP to the two weeks of the DB RWP.

Subjects will complete a daily cataplexy frequency diary each night prior to bedtime to record the number of cataplexy attacks that they had that day beginning at Study Day 1 up to the end of the DB RWP visit. Daily cataplexy frequency diary will not be collected during OLE.

For subjects with at least one day of cataplexy attack data, the average weekly number of cataplexy attacks over each of the two weeks (see Table 1) of the OL SDP will be calculated as follows:

$$\frac{\text{Total number of cataplexy attacks within the OL SDP period}}{\text{Number of days with non-missing data within the OL SDP period}} \times 7 \text{ days}$$

Average weekly number of cataplexy attacks over each of the two weeks of the DB RWP will be calculated similarly. Additionally, average weekly number of cataplexy attacks by week for each study period (see Table 1) will also be calculated as follows:

$$\frac{\text{Total number of cataplexy attacks within a week}}{\text{Number of days with non-missing data within that week}} \times 7 \text{ days}$$

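### The double-blind diary window includes the date of Visit 16, so an entry made that day before bedtime would count as a full day

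*SAP*

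**What the plan says.** - **Double-blind window.** SAP Table 1 uses "1 < Period Day ≤ Date of Visit 16" for the two weeks combined, and the Week 2 row also ends on the date of Visit 16. A note to the table tells the analyst to use whatever data exist when the period is not exactly 14 days.
- **Day numbering.** SAP 6.1 gives "DB RWP Day= (date of assessment or event – date of randomization) + 1". Randomization is at Visit 15, so Visit 16 two weeks later is Day 15. Table 1 leaves out Day 1.
- **Baseline window.** The stable-dose row is "1 < Period Day ≤ Date of Visit 15", so the date of Visit 15 belongs to baseline.
- **The diary.** Protocol 6.12.7 has subjects complete it "each night prior to bedtime, to record the number of cataplexy attacks that they had each day". SAP 9.8.1.1 repeats the bedtime instruction and runs collection "up to the end of the DB RWP visit", with no diary in the open-label extension.
- **Visit 16.** Protocol 7.1.5 schedules fasting bloods and a diary review, and adds "Provide for a light breakfast, if needed". No clock time is given. Early terminators from the Main Study also complete Visit 16 (Protocol 6.14.2).
- **The rate.** Protocol 9.10.1 and SAP 9.8.1.1 divide total attacks by the number of days with an entry and multiply by 7. Every day with an entry has weight 1, and a day without one has weight 0.

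**The concern.** The two windows look alike in Table 1 but differ at their last day. After Visit 15 the diary continues, so that date can hold an ordinary bedtime entry for a whole day. At Visit 16 collection stops. An entry carrying that date and made by the end of the visit covers only the hours before it, and no rule removes it or reduces its weight.

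Where such an entry exists, the double-blind rate is too low against a baseline of whole days. At stake are the size of the primary estimate and the handling of early terminators. For them one truncated entry is a larger share of the data and can decide which missing-data rule applies.

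**Working it through.** **Inputs.** From the documents: a nominal window of Days 2 to 15, so D = 14 diary days; 65 subjects per arm, difference 17.5 attacks per week, SD 30, two-sided 0.05, t-test (Protocol 9.3, SAP 3.4). Assumed: f, the fraction of the Visit 16 day's attacks captured by the entry, from 0.5 down to 0 as the bound. The documents give no value for f. The true daily rate is taken as constant within the period.

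**The plan's own figure.** Noncentrality = 17.5 / (30 × √(2/65)) = 3.33 on 128 df, giving power of 91.0%. The stated figure of at least 90% reproduces.

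**One subject.** With a part-day entry on the last of D diary days, the double-blind rate is multiplied by k = (D − 1 + f)/D. With no entry that day, the rate rests on 13 full days and k = 1.

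**Treatment difference.** Randomization makes the expected baselines equal, so the expected difference in change is the difference in double-blind rates. It becomes 17.5 × k if every subject in both arms has such an entry with the same f. Power is recomputed with the SD held at 30.

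| f | k (D = 14) | Fall in rate | Difference | Power |
|---|---|---|---|---|
| no part-day entry | 1.000 | 0% | 17.50 | 91.0% |
| 0.50 | 13.5/14 = 0.964 | 3.6% | 16.88 | 88.9% |
| 0.25 | 13.25/14 = 0.946 | 5.4% | 16.56 | 87.8% |
| 0 | 13/14 = 0.929 | 7.1% | 16.25 | 86.5% |

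A subject truly unchanged at 14 attacks per week would show a change of −0.5 (f = 0.5) to −1.0 (f = 0). For the Week 2 average alone, k = (6 + f)/7, a fall of 7.1% to 14.3%.

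**Early termination.** The results below are given for f = 0.5, 0.25 and 0.

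- *Primary rate, three diary days:* k = (2 + f)/3 = 0.83, 0.75, 0.67.
- *BOCF (SAP 9.8.1.3):* it applies only when there are no post-randomization diary data. A single part-day entry on Day 2 displaces it and sets the double-blind rate at f times the true rate: 0.50, 0.25, 0.
- *Multiple imputation (SAP 9.8.1.5):* a week is imputed only if it has no data. With termination on Day 9, the part-day entry is the sole Week 2 value, so Week 2 counts as observed. The mean of the two weeks is (1 + f)/2 = 0.75, 0.63, 0.50 of truth. By the same logic the subject does not count toward the more-than-5% trigger for these analyses.
- *LOCF (SAP 9.8.1.5):* the last daily count is carried forward. With termination on Day 6 and filling to Day 15, there are 4 full days and 10 days at f, so (4 + 10f)/14 = 0.64, 0.46, 0.29 of truth.

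**The case against.** The strongest reply is that the part-day entry may never occur. Subjects are told to write the diary "each night prior to bedtime to record the number of cataplexy attacks that they had that day". One who follows that and stops at Visit 16 has no entry for that date, and the formula then drops the day from numerator and denominator without bias. Protocol 7.1.5 has staff review the diary at the visit; it does not ask for an entry there. Table 1 uses an inclusive visit date for Visits 14, 15 and 16 alike, as an upper limit that admits data without creating them. The diary form (Protocol Appendix 13) is not in the available text, so its instructions for the last day cannot be checked. The SAP also expects discontinuation in the double-blind period to be rare.

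Most of this stands. A reader might infer that the plan builds a downward bias into every subject's double-blind rate, and the documents do not support that. A reader might also infer that the artefact favours JZP-258. The within-arm change on JZP-258 would look slightly too good, but the tested quantity is the difference between arms, and that shrinks.

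The reply does not remove the gap. SAP 9.8.1.1 extends collection to the visit itself. Days 9 to 15 make a seven-day Week 2, and Days 2 to 15 a fourteen-day period, only if the visit date contributes. The window therefore anticipates a count for a date on which a full-day count is not normally collectable, and it gives that count full weight.

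**Conclusion.** The point holds as a conditional defect in the window definition. If an entry dated Visit 16 is made before bedtime, it counts as a full day in the double-blind rate, while the matching baseline date can carry a genuine full day. For a 14-day window this lowers that subject's rate by about 4% to 7%, in either arm, and moves the treatment difference toward zero. The randomized test stays valid. The power loss in the table is an upper range, because it needs every subject to have such an entry and the SD to stay at 30; the loss is smaller if the SD falls with the rate.

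The size rests on the assumed f of 0.5 to 0, equal in both arms, and a constant daily rate. The relative error is much larger for early terminators. Few are expected, but they are the subjects whom BOCF, the weekly imputation and LOCF are meant to handle. A rule is worth stating before unblinding.

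**What to change.** In the double-blind Week 2 and combined two-week rows of SAP Table 1, count an entry dated Visit 16 or Early Termination only if it was completed at bedtime for the whole day. Otherwise, for instance if the time of entry cannot be established, end both windows the day before that visit. Reword the note on periods longer or shorter than 14 days so that it does not readmit part-day entries. Leave the stable-dose rows as they are.

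Apply the same rule wherever diary days are used: in deciding whether a subject has post-randomization data for BOCF, in the weekly values for multiple imputation and its 5% trigger (including Week 1 when termination falls there), and in the daily value that LOCF carries forward.

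The cost is two table rows and a note. At most one diary day per subject is lost, 13 instead of 14 in a nominal period, and nothing is lost where no Visit 16-date entry exists. Under the day-before version, a genuine bedtime entry on that date would be discarded too.
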